1.2 Research Hypothesis

BMS-931699 will have greater clinical efficacy compared to placebo on the British Isles Lupus Assessment Group (BILAG)-based Composite Lupus Assessment (BICLA) score, when added to stable background standard of care in patients with active manifestations of systemic lupus erythematosus (SLE) including, at a minimum, elevated antinuclear antibodies, arthritis, and/or cutaneous manifestations satisfying the BILAG “A” or “B” criteria.

1.3 Objectives(s)

1.3.1 Primary Objectives

To compare the proportion of patients who achieve BICLA response (BICLA response rate) at Day 169.

BICLA is defined as:

- British Isle Lupus Assessment Group improvement, defined as BILAG As at Baseline improved to B/C/D, and BILAG Bs at baseline improved to C/D, and no BILAG worsening in other BILAG organ systems such that there are no new BILAG As or greater than 1 new BILAG B; and
- No worsening in the SLEDAI-2K total score compared to Baseline (defined as no increase in SLEDAI total score); and
- No worsening in the physician's global assessment (MDGA) of disease activity ("no worsening" is defined as less than 10% worsening, equivalent to a 10mm increase on a 100mm visual analog scale [VAS]) compared to Baseline.
- No changes in concomitant medications according to the following criteria:
 - No increase of or addition of a new immunosuppressant agent (azathioprine, mycophenolic acid/mycophenolate mofetil, methotrexate, anti-malarial, leflunomide) over baseline levels.
 - No increase in corticosteroid dose above baseline level outside of those allowed per protocol.

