3.3.1 Inclusion Criteria

1. Signed Written Informed Consent

- a) Subjects must be willing to participate in the study and sign the informed consent.
- b) Subjects must be willing and able to complete all study specified procedures and visits.

2. Target Population

- a) Subjects must have SLE as defined by meeting 4 of the 11 classification criteria of the American College of Rheumatology for the classification of SLE, either sequentially or coincident. The 4 criteria need not be present at study entry, but have occurred at some time during the course of the disease and be documented.

b) Subject Re-screening: This study permits the re-screening of a subject that has discontinued the study as a pre-treatment failure (ie, subject has not been randomized / has not been treated). If re-screened, the subject must be re-consented.

Note (1): If a subject is being considered for re-screening, a full screening visit must be performed again.

Note (2): A subject can only be re-screened once (eg, if re-screening for the same subject fails, no additional re-screening is allowed).

c) At screening:

i) Subjects must have elevated ANA $\geq 1:80$ via immunofluorescent assay at the central laboratory or anti-dsDNA or anti-Sm above the normal level as determined by the central laboratory.

Note: For inclusion criterion 2c-i: If central laboratory results are negative and positive results are documented at the site, a single repeat of the central laboratory values is allowed. If the central laboratory repeat is negative, the patient is not eligible to be randomized.

ii) Subjects must have a SLEDAI ≥ 6 to be eligible. At least 4 of the points must be attributable to clinical criteria including at least one of the following clinical parameters: arthritis, rash, myositis, mucosal ulcers, pleurisy, pericarditis, vasculitis and excluding points from lupus headache and organic brain syndrome. Must be confirmed by the External Adjudication Committee.

Note: On Day 1, the SLEDAI 2K must be ≥ 4 including points from at least one of the following clinical components: arthritis, rash, myositis, mucosal ulcers, pleurisy, pericarditis, vasculitis, and fever and excluding parameters which require central laboratory results (hematuria, pyuria, urinary casts, proteinuria, positive anti-dsDNA, decreased complement, thrombocytopenia and leukopenia). Points from lupus headache and organic brain syndrome are excluded.

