iii) Subjects must have at least one of the following manifestations of SLE, as defined by the BILAG criteria as modified for use in this study, which must be confirmed by the External Adjudication Committee:

(1) BILAG A or B score in the Mucocutaneous body system

(2) BILAG A or B score in the Musculoskeletal body system due to active polyarthritis defined as follows:

(a) “BILAG A”: severe arthritis (BILAG #41) manifested by observed active synovitis in ≥ 2 joints with marked loss of functional range of movements and significant impairment of basic activities of daily living, that has been present on several days cumulatively over the past 4 weeks, including at the time of the screening visit. Basic ADLs are defined as the following activities which require assistance or assistive devices (at least one must be present and documented in source): ambulation, toileting, grooming including bathing, dressing, feeding oneself (not responsive to steroids up to 10 mg/day, antimalarials, NSAIDs).

(b) “BILAG B”: Moderate arthritis or tendonitis or tenosynovitis (BILAG #42) defined as tendonitis/tenosynovitis or active synovitis in ≥ 1 joint (observed or through history) with some loss of functional range of movements which lead to some loss of functional range of motion as manifested by effects on instrumental ADLs (such as cooking, driving, using the telephone or computer, shopping, cleaning, etc.) which has been present on several days over the last 4 weeks and is present at the time of the screening visit.

(3) if only one “B” and no “A” score is present in the Mucocutaneous body system or in the Musculoskeletal body system due to arthritis, then at least one B must be present in the other body systems for a total of 2 “B” BILAG body system scores.

iv) Unless intolerant, subjects must be currently receiving at least one of the following steroid-sparing agents for a minimum of 12 weeks, and at stable dose for at least 8 weeks (56 days) prior to signing consent:

Azathioprine (AZA), chloroquine, hydroxychloroquine, methotrexate (MTX), leflunomide, mycophenolate mofetil/mycophenolic acid*. Subjects must remain on stable dose throughout the study[#].

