All Investigator sites within this study will use an Electronic Data Capture (EDC) tool to submit study data to BMS. Electronic Case Report Forms (eCRFs) will be prepared for all data collection fields at Investigator sites, except for fields specific to Pregnancy Forms. Pregnancy Forms will be submitted to BMS using paper CRFs. Subject Quality of Life Questionnaires will be completed by the subject and the information will then be entered with the EDC tool by the investigational site staff. Physician Global Assessment of disease activity worksheet will be completed by the investigator and will then be entered with the EDC tool. Subject completed Quality of Life Questionnaires will be retained at the investigational site.

Study supplies and documents (eg, electronic Case Reports Forms, patient drug logs, etc.) will be provided to the study center by BMS. Urine pregnancy test kits, laboratory specimen collection kits and instructions for collection will be provided by central laboratory vendor. IVRS worksheets and instruction manuals will be provided by the IVRS vendor.

5.3 *Safety Assessments*

On Day 1, the results of all assessments must be reviewed to assure that eligibility requirements are met before contacting the Central Randomization System for the subject's randomization assignment.

Subjects who discontinue from the double-blind treatment period should have “End of Treatment Visit” procedures performed and should return to the clinical for the “Follow-Up Visit” approximately 42 days after the “End of Treatment Visit”. All procedures required for these visits should be completed as well as collection of concomitant medication information.

All assessments should be performed or administered prior to study drug administration unless otherwise indicated. Furthermore, patient’s assessments (ie FACIT-F, SF-36 and Subject’s Global Assessment) must be performed prior to all other assessments.

Every effort must be made to ensure the same evaluator will complete the assessments for each subject at all visits.

Only data for the procedures and assessments specified in this protocol should be submitted to BMS on a case report form. Additional procedures and assessments may be performed as part of your institutional or medical practice standard of care; however, data for these assessments should remain in the subject’s medical record and should not be provided to BMS, unless specifically requested from the sponsor.

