## **8 CONVENTIONS**

### **8.1 Calculations of Key Measures**

#### **8.1.1 Evaluation of BICLA response**

BICLA response is defined based on the following components:

- British Isle Lupus Assessment Group improvement, defined as BILAG ‘A’s at Baseline improved to ‘B’/‘C’/‘D’, and BILAG ‘B’s at baseline improved to ‘C’/‘D’, and no BILAG worsening in other BILAG organ systems such that there are no new BILAG ‘A’s or greater than 1 new BILAG ‘B’; and,
- No worsening in the SLEDAI-2K total score compared to Baseline (defined as no increase in SLEDAI total score); and,
- No worsening in the physician’s global assessment (MDGA) of disease activity (“no worsening” is defined as less than 10% worsening, equivalent to a 10mm increase on a 100mm visual analog scale [VAS]) compared to Baseline; and,
- No changes in concomitant medications according to the following criteria:
  - No increase of or addition of a new immunosuppressant agent (azathioprine, methotrexate, anti-malarial) over baseline levels

- No increase in corticosteroid dose above baseline level outside of those allowed per protocol.

If a subject failed any of the above criteria above, the BICLA response status of the subjects will be set to non-responder.

For the determination of missing BICLA response status, all subjects who prematurely discontinue from the study medication will be imputed as non-responder at all scheduled efficacy visits subsequent to the point of discontinuation.

If any subject has at most one missing component (e.g. MDGA for BICLA) at a given efficacy visit not due to premature discontinuation, the component-wise response status will be imputed based on the following rules.

- If the given visit is not the last scheduled efficacy visit (Day 169), imputation will depend on the observed responses from the immediate previous efficacy visit and the immediate next efficacy visit within 28 days of the current visit date.
- If the given visit is the last scheduled efficacy visit (Day 169), the imputation will depend on the observed responses at the previous 2 consecutive efficacy visits (within 56 days).
- If a subject has response (at component level) at both efficacy visits, the missing response status at current visit will be imputed as responder. Otherwise, response status will be set to non-responder.

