The BICLA response status (composite) for a subject who has more than one component (e.g. MDGA and SLEDAI-2K are missing for BICLA) missing at a given efficacy visit not due to premature discontinuation will be imputed as non-responder.

After any imputation above or none, if for some reason the BICLA response status still cannot be determined, including the case where baseline data is missing, then its value will be set to non-responder.

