## **8.2 Baseline Measures**

The baseline value is the last assessment taken prior to the first dose of study medication. In general, the baseline value is the assessment taken on study Day 1 before the administration of study medication unless otherwise specified.

If a measurement on Day 1 (baseline) is missing, the last assessment taken at the screening period prior to the first dose of study medication will be used.

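### Does BICLA need a written rule for a subject who has no BILAG A or B on Day 1?

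*Protocol*

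**What the plan says.** **Entry.** Protocol 3.3.1 lists the BILAG requirement under criterion 2c, which is headed as applying at screening: "Subjects must have at least one of the following manifestations of SLE, as defined by the BILAG criteria as modified for use in this study". The definitions that follow call for an A or B in the mucocutaneous or musculoskeletal system, and a second B elsewhere if there is only one B and no A. SAP Appendix 1 also checks this criterion at screening.

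**Day 1.** The same section sets a separate Day 1 floor for another index: "On Day 1, the SLEDAI 2K must be ≥ 4 including points from at least one of the following clinical components". There is no matching note for BILAG. Protocol 5.3 adds a general check: "On Day 1, the results of all assessments must be reviewed to assure that eligibility requirements are met before contacting the Central Randomization System". BILAG is scored again on Day 1 (Protocol Table 5.1-2).

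**Baseline.** SAP 8.2: "In general, the baseline value is the assessment taken on study Day 1 before the administration of study medication". Screening is used only as a fallback: "If a measurement on Day 1 (baseline) is missing, the last assessment taken at the screening period prior to the first dose".

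**Response.** Protocol 1.3.1 gives the BILAG component as "defined as BILAG As at Baseline improved to B/C/D, and BILAG Bs at baseline improved to C/D", with no new A and at most one new B in other systems. SAP 8.1.1 repeats it and adds: "If a subject failed any of the above criteria above, the BICLA response status of the subjects will be set to non-responder". A final fallback assigns non-response "if for some reason the BICLA response status still cannot be determined, including the case where baseline data is missing".

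**The concern.** A subject could have a B at screening, drop to C by Day 1 (screening lasts about 28 days), and be randomized with an observed baseline that contains no A or B. The improvement clause then has nothing to act on. Read literally, the subject passes the BILAG component with no BILAG improvement. Since one new B is allowed, even a course of B at screening, C on Day 1 and B on Day 169 could pass it. A programmer who gives weight to the word improvement, or who treats the status as undeterminable, would instead code a non-responder.

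If both codings are open, the primary response rate depends on a choice that is not written down, and the same derivation feeds the Day 85 futility analysis. The planned tables would not expose it: SAP 7.3.2 tabulates baseline BILAG and SAP 7.5.1 gives reasons for non-response, but responders are not split by whether they had an A or B on Day 1.

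**Working it through.** **1. What the text implies.** The component is a list of conditions on baseline As, baseline Bs and new grades. SAP 8.1.1 makes a non-responder of anyone who fails a listed criterion. A subject with no baseline A or B fails neither improvement condition, and the limits on new As and Bs can be evaluated. The final fallback is for a status that cannot be determined. Here the Day 1 BILAG is observed, so the fallback does not clearly apply. The literal reading is therefore an answer, though not one the authors spelled out.

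**2. Reproduce the planned power.** Protocol 8.1 and SAP 5 give n = 70 per arm, a one-sided 0.05 continuity-corrected chi-squared test, 25% on placebo, and power of at least 89% (against 50%) and 74% (against 45%).

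Effective size with the correction: n′ = n − 2/d + 1/(n·d²).

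- d = 0.25: n′ = 70 − 8 + 0.229 = 62.23, power 90.0% (exact enumeration 89.8%).
- d = 0.20: n′ = 70 − 10 + 0.357 = 60.36, power 75.0% (exact 74.7%).

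The plan's figures reproduce.

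**3. Size of the coding choice.** Let f be the share of each arm with no Day 1 A or B, and q their response rate under the literal coding. Neither is in the documents; f = 2–10% and q = 60–80% are assumptions, with q equal in both arms. All other subjects respond at 25% and 50%.

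- Literal coding: arm rate = (1 − f)·p + f·q.
- Non-responder coding: arm rate = (1 − f)·p.
- Gap between codings, per arm: f·q.
- Expected difference under both: (1 − f)·25 points.

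| f | Gap per arm (points) | Subjects of 70 | Expected difference, both codings | Power, literal | Power, non-responder | Power, restricted to Day 1 A/B |
|---|---|---|---|---|---|---|
| 2% | 1.2–1.6 | 0.8–1.1 | 24.5 | 88.5–88.6% | 89.0% | 89.5% (n = 69) |
| 5% | 3.0–4.0 | 2.1–2.8 | 23.75 | 86.2–86.4% | 87.5% | 88.1% (n = 66) |
| 10% | 6.0–8.0 | 4.2–5.6 | 22.5 | 81.8–82.3% | 84.6% | 86.6% (n = 63) |

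Example, f = 5% and q = 60%: placebo 0.95 × 25 + 0.05 × 60 = 26.75%; active 0.95 × 50 + 0.05 × 60 = 50.5%; difference 23.75 points.

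**4. How much of the power loss comes from the coding.** At f = 5%, power falls from 90.0% by 3.5 to 3.8 points under the literal coding and still by 2.5 points under the non-responder coding. So about two thirds of the loss comes from having such subjects at all, and no coding rule recovers it. The coding itself moves power by 1.0 to 1.3 points.

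**5. Drop the assumption of no drug effect in this group.** Suppose these subjects respond at 60% on placebo and 70% on active.

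- f = 5%: 26.75% against 51.0%, literal power 87.7%, against 87.5% for the non-responder coding.
- f = 10%: 28.5% against 52.0%, literal power 85.3%, against 84.6%.

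The order reverses, so no coding wins in general on power.

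**6. Direction.** Day 1 status is fixed before the first dose, and either rule would be applied alike in all arms. Under equal response the literal coding raises both rates and dilutes the contrast. It does not favour the drug.

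**The case for a change.** The strongest opposing case is that a primary endpoint should leave no coding choice to the programmer, and that this one costs a sentence to settle. The entry criterion is worded for screening, the deviation check looks only at screening, and where the authors wanted a Day 1 floor they wrote one, for SLEDAI-2K. At a 5% share, f·q / ((1 − f) × 25% + f·q) puts 11–14% of placebo responders among subjects with no Day 1 A or B to improve, which sits badly with a component described as improvement.

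The omission stands as a matter of drafting. The rest is weaker. The SLEDAI-2K note lowers a screening threshold of 6 to 4 and drops items that need central-laboratory results. It can be read as a relaxation, and the absence of such a note for BILAG could mean that the A/B criterion is not relaxed. Protocol 3.3 requires the entry criteria to be met before Day 1 dosing, without exception. That reading is arguable, but it means the affected group may be close to empty. The four-week BILAG look-back (Protocol 5.4.2.1) and the prednisone reduction before Day 1 (Protocol 4.5.3) point the same way. The rule may also sit in BILAG Appendix 4, the Adjudication Charter or the Interim Analysis SAP, none of which could be seen.

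The remedy usually suggested, coding these subjects as non-responders, would replace the literal reading of the protocol definition with a narrower one. It would also remove any real response among subjects who had clinical activity on Day 1.

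**Conclusion.** No change follows. The documents do not name this case, but the definition as written classifies it. Both candidate codings treat the arms alike, and the expected treatment difference is the same under each if response in this group does not depend on treatment. On the assumed range (2–10% affected, 60–80% responding), the choice moves each arm's rate by 1.2 to 8 points and power by about 0.4 to 2.9 points, and the sign of the power change depends on whether the drug works in these subjects. Literal coding, non-response and exclusion are all defensible, and competent statisticians would differ.

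The real share could be zero, and a share well above 10% would make the choice weigh more in the reported rates. Recording the coding before unblinding, with a count of such subjects by arm, would be good housekeeping. The trial's conclusion does not depend on it, and no power gain should be claimed for it.

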1.3.2 Secondary Objectives

Short-term period Part 1 only:

- To evaluate the safety and RO when 6 to 10 subjects per arm reach 29 days (4 weeks).

Short-term period Part 1 and Part 2:

To assess:

- The safety and tolerability of treatment with BMS-931699 in patients with active SLE
- The proportion of patients who meet response criteria for the SLE Responder Index(4) [SRI(4)], SRI(5) and SRI(6) at Day 169.

Note: An SRI(X) Response is defined as:

- a reduction in Day 1 SLEDAI-2K disease activity score of $\geq X$ points;
- no worsening of disease (defined as an increase of ≥ 30 mm on a 100mm VAS from Day 1 as measured by the MDGA; and
- no new BILAG-2004 Index A organ system score and no more than one new or worsening BILAG-2004 Index B organ system scores

- The proportion of patients with SLE Responder Index [SRI(4), SRI(5) and SRI(6)] at Day 85.
- The proportion of patients with a BICLA response at Day 85.
- The improvement in the extent of cutaneous and mucous membrane activity, as measured by the Cutaneous Lupus Erythematosus Disease Area and Severity Index (CLASI) at Day 85 and Day 169

- Joint tenderness and swellings as measured by the by American College of Rheumatology (ACR)28 at Day 85 and Day 169
- The other indices of SLE activity measured at Days 29, 57, 85, 113, 141 and 169 including:
 - The change from baseline in overall BILAG-2004 score. A major response is defined as described in Yee et al 2010 (A=12, B=8, C=1, D/E=0).¹¹
 - The change in overall Systemic Lupus Erythematosus Disease Activity Index 2K score (SLEDAI 2K)
 - The change from baseline in Physician's Global Assessment of disease activity (MDGA) score
- The systemic exposure of BMS-931699 in patients with SLE
- The cumulative corticosteroids use and immunosuppressants use over time
- The immunogenicity of BMS-931699
- Serum biomarkers C3, C4, anti-double-stranded deoxyribonucleic acid (anti-dsDNA), anti-nuclear antibody (ANA) and other autoantibodies at Day 85 and Day 169
- The pharmacodynamics (PD) of BMS-931699, including assessments potentially associated with target engagement [including receptor occupancy (RO)].

Note: Although all efforts must be made to collect all RO samples required per protocol, it may not be possible for a site to obtain samples from subjects located in certain participating regions due to stability and processing issues. Site **MUST** consult with the Medical Monitor prior to deciding not to collect RO samples.

1.3.4 Long-Term Extension Period Objectives

Assess the long term clinical safety, tolerability and efficacy of lulizumab pegol.

similar to the reported plasma volume, indicating very limited extravascular distribution. The [REDACTED]

[REDACTED]

[REDACTED]

[REDACTED]

[REDACTED]

[REDACTED]

[figure not shown]
[figure not shown]
[REDACTED] 16

[REDACTED]

[REDACTED]

[REDACTED]

The MAD study IM128003 was performed in 24 subjects (3 cohorts of 8 subjects) treated for

Intense safety monitoring will be put in place during the entire study (short-term and long-term extension periods), allowing early detection of any safety signals. Specifically, the following measures will be put in place:

- Patients will undergo safety evaluation at each clinic visit.
- Investigator will conduct safety evaluation before dosing.
- Continuous internal data review by unblinded clinical monitoring team.
- Monitoring team to refer to independent external DMC any safety issue deemed to be of relevance.
- Independent external DMC to meet at regular intervals throughout the entire study to review all data (frequency to be determined in conjunction with DMC).
- Stopping rules to be implemented under DMC guidance.

DMC and internal safety monitoring activities initiated in Part 1 will continue into Part 2 and will be ongoing until the end of the study, including the long-term extension.

In summary, the potential overall benefit ratio for BMS-931699 treated subjects in this trial appears favorable. In order to minimize the overall risk to participating subjects, this protocol has inclusion and exclusion criteria appropriate to the population and proposed treatments, exclusionary screening tests [chest x-ray, Quantiferon Gold testing (or other interferon gamma release assay test, such as T-SPOT) wherever appropriate, risk factor/age specific breast screening, medical history], and specific follow-up safety assessments. In addition, the AEs and SAEs will be reviewed on an ongoing basis by the medical monitors and pharmacovigilance group to look for trends and any safety issues.

